3.0 OUTCOMES

3.1 Primary Outcome

Atrial fibrillation or atrial flutter of at least 30 seconds duration on an ambulatory ECG patch monitor.

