7.4.2 Procedures for ECG patch wear

The BioTelemetry ePatch Monitor will be used for ambulatory ECG monitoring. The battery life with a single channel recording is 7 days. The participant will be instructed to wear the ePatch for up to 7 days. However, the data collected from a participant will be considered adequate for a participant with a minimum analyzable time of 1 hour.

BioTelemetry will send participants, via courier, an ambulatory ECG monitoring kit containing one sensor and two adhesive patches. If the adhesive patch is no longer functional, the sensor

This document contains information that is privileged or confidential and may not be disclosed unless such disclosure is required by applicable laws and regulations. The information in this document is the property of Apple Inc. and may not be reproduced, published, or disclosed to others without written authorization from Apple Inc.

can be moved to the backup adhesive patch. At the end of the recording period, the participant will be required to mail the monitor back to BioTelemetry using the supplied prepaid mailer.

In the event it is discovered that the participant never received the ePatch due to a shipping error or became lost in transit, then BioTelemetry will issue a second ePatch to that participant. Any subsequent loss of ePatches will not be replaced.

Approximately 14-20 days after enrollment it is expected that most participants will have completed wearing the patch for up to 7 days and will have returned the patch to BioTelemetry via a provided tracked USPS mailer. The ambulatory ECG monitor should be received by BioTelemetry within 45 days from enrollment. Those who return patches beyond 45 days after enrollment or do not begin wearing their patch within 14 days of patch shipment will be included in the fall-out subgroup, however they will still be eligible for a follow-up visit with the Study Telehealth Provider. Those who never return the ambulatory ECG monitor will also be placed in the fall-out subgroup.

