4. ANALYSIS METHODS

4.1 General Principles

Method for Constructing Confidence Intervals

We will construct confidence intervals using the asymptotic Gaussian approximation. For proportions near 1 or 0, a potential drawback of this method is confidence intervals containing values outside of the range [0,1]. If we encounter confidence intervals with bounds outside of the [0,1] range we will instead construct the confidence intervals using the bias corrected and accelerated (BCa) method of creating a bootstrap confidence interval.

Incomplete Dates

If only the year of a date is given (YY), then the date shall be set to 'YY0701'. If only the year and month of a date is given (YYMM), then the date shall be set to 'YYMM15'.

Descriptive Statistics

Numerical variables will be summarized using standard summary statistics including the number of participants, mean, standard deviation, median, 10th and 90th percentile and range (i.e., minimum and maximum) as appropriate. For categorical data, proportions will be presented in a frequency table format.

Multiple Patches per Participant

In rare instances where a single user ID is associated with data available from more than one patch, only data from the final patch will be used in statistical analyses.

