4.5 Definitions

Irregular Arrhythmias

AF is defined as irregular QRS complexes with no clearly discernible p-waves lasting 30s or more ever during the ECG monitoring. In tertiary analyses, we consider definitions requiring longer periods of AF, up to 24 hours.

Sinus arrhythmia is defined as a beat-to-beat variation lasting at least 120ms with discernible sinus p-waves ever during the ECG monitoring.

Frequent PACs are defined as p-waves that are observed before the predicted time interval. A participant is considered to have frequent PACs if they average 30 or more PACs/hour during the ambulatory ECG monitoring.

Frequent PVCs are defined as wide QRS complexes without preceding p-waves. A participant is considered to have frequent PVCs if their (total number of PVCs/total number of beats)*100% is $\geq 5\%$ and very frequent PVCs if $\geq 15\%$ during the ambulatory ECG monitoring. (See the next subsection for criteria used to indicate presence of PACs and PVCs at the tachogram-level.)

Intermittent heart block is defined as the presence of p-waves that are not followed by a QRS complex and are not preceded by a gradually prolonging PR interval. No minimum amount of time is required.

Multifocal atrial tachycardia is defined as an irregular, narrow complex tachycardia with discernable preceding p-waves preceding the QRS complex that are of at least two different morphologies, lasting at least 30 seconds.

Atrial tachycardia with variable conduction is defined as an irregular narrow complex tachycardia with one predominant p-wave morphology lasting at least 30 seconds. The p-waves are followed by QRS complexes with varying ratios, from one QRS for every p-wave, to one QRS for multiple p-waves. The p-waves are a distinct morphology from typical flutter waves.

Notification Concordance

The ambulatory ECG monitoring will be considered to be concordant with either an IRN or ECG app-AFib classification before enrollment if 30 seconds of AF is observed on the ambulatory ECG monitor during the period of wear in the study for study participants with at least 1 hour of usable ECG monitor data.

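### The final-patch rule in SAP 4.1 conflicts with the AF definition in SAP 4.5 and can count a participant with AF on a valid earlier patch as negative; the effect is very small

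*Combined protocol and SAP*

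**What the plan says.** SAP 4.1, under Multiple Patches per Participant, covers the case directly. When one participant has several recordings, which the SAP expects to be rare, "only data from the final patch will be used in statistical analyses". It gives no reason and makes no exception for AF on an earlier patch.

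Three other places define the outcome without that restriction:
- SAP 4.5 defines AF as an episode "lasting 30s or more ever during the ECG monitoring".
- SAP 4.5 also calls the patch concordant with the notification "if 30 seconds of AF is observed on the ambulatory ECG monitor during the period of wear in the study".
- Protocol 3.1 sets the primary outcome as "Atrial fibrillation or atrial flutter of at least 30 seconds duration on an ambulatory ECG patch monitor".

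Protocol 7.4.2 limits how a participant could come to have two patches. A second ePatch is sent "In the event it is discovered that the participant never received the ePatch due to a shipping error or became lost in transit", and after that "Any subsequent loss of ePatches will not be replaced". Each kit holds "one sensor and two adhesive patches", so changing the adhesive does not create a second recording.

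**The concern.** With an outcome of the 'ever' type, discarding part of a participant's monitoring can remove AF but cannot add it. A participant with AF on a valid earlier patch, and a final patch that is long enough to analyse and free of AF, meets the SAP 4.5 definition yet enters the numerator as zero. SAP 4.7 already warns that wearing the patch after the notification tends to understate AF, and this rule pushes the same way.

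A second gap concerns who is analysed. SAP 3 admits to the EAS anyone who returns an ePatch with an hour of usable data, without saying which patch. SAP 4.6 treats a participant with under an hour of analysable time as missing. If the earlier patch ran for days and the final one for minutes, these two sections and SAP 4.1 give no single answer.

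Neither the sensitivity analyses in SAP 4.3, which vary the minimum wear time, nor the limitations in SAP 4.7 mention the rule. At stake is a clean definition of the outcome, so that nobody has to choose between two written rules once results are known. The main findings are not at stake.

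**Working it through.** **1. Scale: reproduce the plan's precision figures.** Inputs from SAP 1.3: 400 returned patches per primary group, 95% confidence, worst case p = 0.5. Width = 2 × 1.96 × √(p(1 − p)/n).
- n = 400: 2 × 1.96 × √(0.25/400) = 0.0980 (plan: no more than 0.10)
- n = 300: 0.1132 (plan: 11.3%)
- n = 200: 0.1386 (plan: 13.9%)

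The figures reproduce. The half-width at n = 400 is 0.0980/2 = 0.049, or 4.9 points.

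**2. Where the rules agree and where they part.** For a participant with AF on a valid earlier patch:

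| Final patch | SAP 4.5 read over all wear | SAP 4.1 final patch only |
|---|---|---|
| One hour or more, AF seen | AF | AF |
| One hour or more, no AF | AF | no AF |
| Under one hour | AF, if admitted to the EAS | missing under SAP 4.6; EAS status unsettled |

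Only the second row misclassifies someone who stays in the denominator.

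**3. Effect of one discordant participant.** 1/400 = 0.25 points, or 0.25/4.9 = about 5% of the half-width. In a group of another size the effect is 100/n points. As an illustration, assume 120 of 400 with AF (30.0%, exact 95% CI 25.5% to 34.8%). Moving two people from negative to positive gives 122 of 400 (30.5%, 26.0% to 35.3%).

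**4. Effect on the estimate.** The documents give neither the share of participants with two recordings nor the share of those with AF only on the earlier one. Both are assumptions here. Shift in points = 100 × (share with two recordings) × (share of those discordant); people per 400 in brackets.

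| Share with two recordings | 10% discordant | 30% discordant | 50% discordant |
|---|---|---|---|
| 0.5% | 0.05 (0.2) | 0.15 (0.6) | 0.25 (1) |
| 1% | 0.10 (0.4) | 0.30 (1.2) | 0.50 (2) |
| 2% | 0.20 (0.8) | 0.60 (2.4) | 1.00 (4) |
| 5% | 0.50 (2) | 1.50 (6) | 2.50 (10) |

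A share of 1% or less fits the SAP's description best, and there the shift is at most 0.5 points. The 5% row is hard to square with that description or with the replacement rule in Protocol 7.4.2.

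**5. Final patch under one hour.** Starting again from the assumed 120/400 = 30.00%, suppose one such participant is removed. If the earlier patch showed AF, the estimate becomes 119/399 = 29.82%, a fall of 0.18 points. If it showed none, it becomes 120/399 = 30.08%, a rise of 0.08 points. The direction depends on who is removed.

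**The case against.** The strongest reply is that the situation hardly arises. Under Protocol 7.4.2 a replacement goes out only when the first patch did not arrive or went missing in transit, and only once. Two usable recordings from one person would need something unusual, such as a missing patch that later turns up. This stands, and it is the main reason the point is minor.

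Second, a mis-shipped first patch might have been worn by somebody else. The documents do not say this happens, but neither do they say that every earlier recording is known to belong to the participant. So any repair should require confirmation of whose recording it is. This stands as a condition on the fix; it does not justify preferring the last patch as such.

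Third, using one patch keeps observation time comparable. This carries little weight, because analysed wear already runs from one hour to 7 days. It does argue for capping pooled time at 7 days.

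Fourth, SAP 4.1 could be read as choosing the recording and SAP 4.5 as defining AF within it. That reading is possible, but SAP 4.5 speaks of the whole period of wear in the study and nothing in the SAP states the link.

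A reader might infer more than the text supports: that all AF on an earlier patch is lost, that the bias is always downward, or that the rule has nothing in its favour. The first fails when the final patch also shows AF, or when the participant becomes missing. The second fails for participants removed because of a short final patch. The third overlooks that the rule is prespecified, blind to outcome and simple.

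**Conclusion.** The conflict is real and unaddressed, but narrow. Among participants retained in the EAS, the final-patch rule can only lower the AF proportion in Objectives 1a, 1b, 2b and 2c, and only through those with AF on a valid earlier patch and an analysable, AF-free final patch. For those whose final patch is under an hour, membership of the EAS is undefined and the direction of any effect is open.

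The size is firm per person (0.25 points at n = 400) and assumed in total (at most 0.5 points if 1% or fewer have two recordings and half of those are discordant). The documents contain no multi-patch rate, so the total cannot be pinned down further. Nothing here supports inferring that a primary result is in doubt. This is a consistency correction worth making before analysis.

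**What to change.** Replace the sentence in SAP 4.1 with a rule such as: *If a participant has more than one patch recording confirmed as theirs and meeting the timing rules, AF is present if seen on any of them within a combined total of up to 7 days of wear, and the 1-hour minimum applies to the summed analysable time.* State that recordings are taken in the order worn, so that the cap leaves no choice, and refer to the rule in the EAS definition (SAP 3) and in SAP 4.6.

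Report the number of participants with more than one recording, and how many change AF status or EAS membership compared with the final-patch rule. If the final-patch rule is kept instead, SAP 4.5 and SAP 3 should say so, with the reason and the same counts.

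The cost is one SAP sentence and two cross-references, a check that each recording belongs to the participant, and adjudication of the earlier recording if that has not been done. A few participants would be observed slightly longer than under the final-patch rule, within the 7-day limit.

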4.2 Study Population

Participant Disposition

The number and percent of participants who completed the study, discontinued from the study, and reasons for discontinuation from the study will be summarized by age group, participant classification (i.e., IRN, ECG App classification of AFib, or ECG App classification of inconclusive) and overall, for the FAS (table shown by age for illustrative purposes).

Age group, yrs	Measures	IRN	ECG: AFib	ECG: inconclusive
< 55	N Completed the study, n (%) Discontinued from study, n (%) Reasons for discontinuation			

55-64	N Completed the study, n (%) Discontinued from study, n (%) Reasons for discontinuation			
65+	N Completed the study, n (%) Discontinued from study, n (%) Reasons for discontinuation			
Overall	N Completed the study, n (%) Discontinued from study, n (%) Reasons for discontinuation			

Participants having protocol deviations will be summarized using the FAS population.

Age group, yrs	FAS, N	Protocol deviations, n (n/N)
<55		
55-64		
65+		
Overall		

Demographic and Other Baseline Characteristics

Demographic and other baseline characteristics will be summarized overall, by age, and by participant classification using the EEAS and EAS. No statistical tests will be performed for comparison of any baseline measurement by age group.

All summaries of continuous characteristics will be based on non-missing observations and the percent of participants missing values will be reported. For categorical characteristics, percents will be calculated out of the total number of participants in the data set (i.e., each denominator includes the number of participants with missing/unknown values for the variable), where the percentage missing will also be reported.

Table 2 Summaries of Demographic and Other Characteristics at Baseline.

Characteristic	Summarized as	Categories
Age	Categorical and Continuous	<55, 55-64, 65+ years
Gender	Categorical	Female Male Non-binary
Race/Ethnicity	Categorical	American Indian or Alaska Native Asian Black or African American Hispanic, Latino or Spanish origin Middle Eastern or North African Native Hawaiian or Other Pacific Islander White Some other race, ethnicity or origin Prefer not to respond
BMI	Categorical and Continuous	<30 kg/m ² and ≥30 kg/m ²
Average number of cigarettes smoked per day	Categorical	None 1-10 11-20 21-40 41 or more Rather not say
Average number of alcoholic beverages consumed per week	Categorical	Less than 1 1-5 6-9 10 or more Rather not say

Medical History	Categorical	High blood pressure or hypertension Diabetes mellitus Heart attack or myocardial infarction Heart failure Stroke or transient ischemic attack Peripheral arterial disease Ever diagnosed you with atrial fibrillation or atrial flutter
Told by doctor had a type of irregular heart beat	Categorical	Atrial Tachycardia Frequent Premature Ventricular Contractions (PVCs) Frequent Premature Atrial Contractions (PACs) Supraventricular Tachycardia (SVT) Ventricular Tachycardia (VT) None of the above I don't know
Currently taking medications	Categorical	Aspirin Warfarin (coumadin) Apixaban (Eliquis) Dabigatran (Pradaxa) Edoxaban (Savaysa) Rivaroxaban (Xarelto) None of these
Notification received	Categorical	Irregular rhythm notification ECG app on Apple Watch result of "Atrial Fibrillation" ECG app on Apple Watch result of "Inconclusive" ECG app on Apple Watch result of "Heart Rate over 120" ECG app on Apple Watch result of "Heart Rate under 50" I'm not sure
How would you rate your physical health	Categorical	Excellent Very good Good Fair Poor

To what extent are you able to carry out your everyday physical activities	Categorical	Completely Mostly Moderately A little Not at all
How would you rate your mental health	Categorical	Excellent Very good Good Fair Poor
How would you rate your satisfaction with your social activities and relationships	Categorical	Excellent Very good Good Fair Poor

Medications at study visits 1 and 2

Medications reported during study visit 1 and 2 will be summarized using the EEAS group by drug category or generic drug name by age group and overall. We will also describe new medications started between SV1 and enrollment and SV2 and SV1.

Drug Category or Name	N Responding SV1 (%)	N on Medication SV1 (%) [*]	N Responding SV2 (%)	N on Medication SV2 (%) [*]
Beta blockers				
Calcium channel blockers				
Aspirin				
Anticoagulants				

* Percent calculated as percent of participants who responded to whether they used the corresponding drug type.

4.3 Analysis Methods

Analysis of the Primary Endpoint Addressing Objective 1a and 1b

For Objectives 1a and 1b we have designed the study to estimate the proportion of participants diagnosed with AF within a 0.10 confidence interval width.

Objective 1a – The proportion of participants with an IRN prior to enrollment who have AF confirmed by ambulatory ECG patch monitoring.

This proportion will be estimated as the ratio of the number of participants in the EAS who have atrial fibrillation or atrial flutter of at least 30 seconds duration on patch wear and received an IRN before enrollment, divided by the number of participants in the EAS who received an IRN before enrollment. An exact 95% two-sided confidence interval will also be presented. We will also describe the number of participants who received an IRN before or during enrollment with arrhythmias other than atrial fibrillation.

Objective 1b Analysis – The proportion of participants with an ECG app-AFib classification prior to enrollment who have AF confirmed by ambulatory ECG patch monitoring.

This proportion will be estimated as the ratio of the number of participants in the EAS who have atrial fibrillation or atrial flutter of at least 30 seconds duration on patch wear and received an ECG app-AFib classification before enrollment divided by the number of participants in the EAS who received an ECG app-AFib classification before enrollment. An exact 95% two-sided confidence interval will also be presented. We will also describe the number of participants who received an ECG app-Fib before enrollment with arrhythmias other than atrial fibrillation.

Analysis of the Secondary Endpoints Addressing Objectives 2a, 2b and 2c

Objective 2a Analysis - The proportion of participants with an IRN or ECG app-AFib classification reporting contact with a non-study healthcare provider at 15 and 60 days after study enrollment.

This proportion will be estimated as the ratio of the number of participants who received an IRN or ECG app-AFib classification in the EEAS who reported contact with a non-study healthcare provider at 15 (and separately at 60) days after study enrollment divided by the number of participants in the EEAS who received an IRN or ECG app-AFib. An exact 95% two-sided confidence interval will also be presented.

Objective 2b Analysis

This proportion will be estimated as the ratio of the number of participants in the EAS who have atrial fibrillation or atrial flutter of at least 30 seconds duration on patch wear and received an ECG app-Inconclusive status before enrollment, divided by the number of participants in the EAS who received an ECG app-Inconclusive status before enrollment. An exact 95% two-sided confidence interval will also be presented. We will also describe the

number of participants who received an ECG app-Inconclusive status before enrollment with arrhythmias other than atrial fibrillation.

Objective 2c Analysis

This proportion will be estimated as the ratio of the number of participants who have atrial fibrillation or atrial flutter of at least 30 seconds duration on patch wear who are greater than 65 years of age at enrollment divided by the number of participants enrolled who are greater than 65 years of age at enrollment using the EAS. An exact 95% two-sided confidence interval will also be presented. We will also describe the number of participants who are 65 years of age or older at enrollment with arrhythmias other than atrial fibrillation. A similar proportion will be presented for those less than 65 years of age at enrollment.

Sensitivity and Sub-analyses

The proportions and 95% confidence intervals for Objectives 1a and 1b will be performed separately by age group (<55, 55-64, ≥ 65), sex, race/ethnicity, cohort status determined at enrollment, cohort status determined during patch wear (e.g., received an IRN during patch wear, received an ECG app-Inconclusive classification during patch wear) and selected medical history conditions (e.g., ever diagnosed you with atrial fibrillation or atrial flutter, or ever had a stroke, Transient Ischemic Attack (TIA) or “Mini Stroke”). Chi-squared tests will be performed to determine if proportions differ significantly by subgroup.

Baseline demographics and medical history, survey results, and adverse events will be summarized using descriptive statistics for the FAS. Baseline demographics and medical history will also be summarized for participants in the FOG.

Additional analyses may be performed to gain further insight into the relationships between receiving notifications or app-based classifications and ePatch data. Importantly, we will additionally evaluate use of the IRN and ECG app features and behavioral response to notifications as captured in the 15 day PRO. Similarly, we will evaluate behavioral response to engaging a healthcare provider as captured in the 60 day PRO by relevant participant characteristics.

To understand the sensitivity of our findings for study objectives utilizing the EAS that requires at least 1 hour of useable data from participants in the EEAS, we will vary the requirement that participants with less than 1 hour of wear time be considered as missing their ECG data. We will also conduct additional sensitivity analyses considering the following alternative minimum wear times: 6 hours, 1 day, 2 days, and 5 days.

Adverse Events

A participant will be counted once for a reported AE even if the participant had multiple occurrences of that AE. We will summarize the proportion of participants reporting anxiety and rash in the EEAS and EAS. All AEs will be collected; however, these AEs are of most interest to the study device (anxiety) and are highest risk in the study (rash).

Adverse Events	N EEAS	% EEAS	N EAS	% EAS
Anxiety				
Rash				

The participant incidence of all serious adverse events will be presented for each analysis set by age group and overall.

Age group, yrs	N SAEs	N unique participants with SAEs	SAEs/participants with SAEs
< 55			
55-64			
65+			
Overall			

Analysis of Fall-Out Subgroup

The FOG (a subset of the FAS) will include participants who are enrolled but otherwise do not complete the study. Possible reasons are listed in Section 3. We will describe baseline characteristics for this group and for those in the FOG that have completed the PRO, we will report rates of contact with a non-study healthcare provider.

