7.5 Procedures for Apple Watch wear

Participants will be asked to wear their Apple Watch as they would with normal use.

Participants with a Series 4 Apple Watch will be asked to take an ECG at least 2 times each day while wearing the ECG patch. In addition, participants will be asked to take an ECG app recording after receiving each irregular rhythm notification.

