10.3.3 Subgroup Analyses

The proportions and 95% confidence intervals for the primary outcomes (study objectives 1a and 1b) will be performed separately by age group (<55, 55-64, ≥ 65), sex, and race/ethnicity, cohort status determined at enrollment, and cohort status determined throughout the observations period (e.g., received an IRN during patch wear, received an ECG app-Inconclusive classification during patch wear). Chi-squared tests will be performed to determine if these proportions differ significantly by subgroup.

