3. ANALYSIS SETS

The Full Analysis Set (FAS) will consist of all enrolled participants who complete the informed consent process. This analysis set will be used to summarize subject demographics, medical history, adverse events, self-reported health status, diagnosis, and contact with the health care provider.

The ePatch Eligibility Analysis Set (EEAS) will consist of those in the FAS deemed eligible to receive an ePatch at Study Visit #1. This analysis set will be used to assess Objective 2a.

The ePatch Analysis Set (EAS) will consist of all those in the EEAS who receive and return an ePatch with at least 1 hour of usable data and who do not belong to the Fallout Subgroup. This analysis set will be used to assess Objectives 1a, 1b, and 2b and 2c. We will repeat these analyses in the EEAS as a sensitivity analysis using appropriate methods for handling missing data.

The Fallout Subgroup Analysis Set (FOG) will consist of participants who enroll and complete the informed consent process but otherwise do not complete the study. Reasons for study incompleteness include; failure to contact Study Telehealth Provider within 30 days of enrollment, being deemed ineligible at Study Visit #1 for ePatch wear due to emergent symptoms, ePatch not returned within 45 days of enrollment, failure to start wearing ePatch within 14 days of shipment, unable to verify at Study Visit #1 a study eligible IRN or ECG-app notification, study withdrawal (i.e., withdrawal of consent), or lost to follow-up (i.e., death). We will present demographic and medical history information for this analysis set.

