4.7 Potential Limitations and Mitigation Strategies

We have identified several potential limitations in our planned analyses and have planned various sensitivity analyses and alternate approaches to understand and mitigate the impact of these limitations on our findings. The ePatch is not worn at the time of the initial notification and we may not detect AF on the subsequent ambulatory ECG monitoring, particularly in participants with low burden AF. We additionally expect that some participants will wear their ePatch for a period shorter than 7 days. We acknowledge that several factors may contribute to an overestimated or underestimated proportion of AF in participants who receive an IRN or ECG app-AFib classification. We describe above sensitivity analyses to evaluate the sensitivity of estimates to the minimum wear time for inclusion in the analysis (described in Section 4.3).

In particular, we anticipate several biases that may impact the estimates for Objectives 1a, 1b, 2b and 2c.

- **Patch Wear Bias:** We anticipate that not all participants will wear their patches for the full 7 day wear period. We acknowledge that wear periods shorter than 7 days and a study design where the ePatch is worn during a period that follows the initial notification (and not simultaneously) will likely contribute to an underestimated true proportion of AF in participants who receive an IRN or ECG app-AFib classification because the AF that triggered the initial notification may not be detected during the subsequent ambulatory ECG monitoring. We will evaluate the sensitivity of our estimates addressing Objectives 1a, 1b, 2b and 2c to the minimum wear time for inclusion in the analysis (described in Section 4.3).

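### The chi-squared tests of AF by a watch result received during patch wear ignore wear time, so a difference cannot be put down to a link between the result and AF alone

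*Combined protocol and SAP*

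**What the plan says.** SAP 4.3, under Sensitivity and Sub-analyses, repeats the Objective 1a and 1b proportions by several factors. Most are fixed before the patch goes on (age, sex, race/ethnicity, medical history). One is not: "cohort status determined during patch wear (e.g., received an IRN during patch wear, received an ECG app-Inconclusive classification during patch wear"). For all of them, "Chi-squared tests will be performed to determine if proportions differ significantly by subgroup". Protocol 10.3.3 has the same rows and the same test: "Chi-squared tests will be performed to determine if these proportions differ significantly by subgroup". Neither section names an adjustment or stratification.

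SAP 4.5 counts AF "lasting 30s or more ever during the ECG monitoring". On wear, protocol 7.4.2 states: "The participant will be instructed to wear the ePatch for up to 7 days". SAP 3 admits to the EAS those who "receive and return an ePatch with at least 1 hour of usable data" and are not in the fallout subgroup. SAP 4.7 expects unequal wear: "We anticipate that not all participants will wear their patches for the full 7 day wear period".

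Protocol 7.5 asks Series 4 users for at least two ECGs a day during wear. In addition, "participants will be asked to take an ECG app recording after receiving each irregular rhythm notification".

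SAP 4.3 also plans sensitivity analyses with minimum wear of 6 hours, 1, 2 and 5 days for objectives that use the EAS. It does not say that the subgroup tests are repeated in them.

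**The concern.** A chi-squared test asks whether two classifications are independent across the whole sample. Here both accumulate over the same period. A participant who wears the patch for a few hours has little chance of showing AF and little chance of an Inconclusive result or an IRN while wearing it. A participant who wears it for 7 days has more chance of each. Pooling the two creates an association even if, at any given length of wear, the result says nothing about AF. Age and sex do not have this problem.

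The ECG-app rows have a second route. If participants in AF receive more IRNs, they are asked for more ECGs and so have more chances of at least one Inconclusive result. This cannot affect the row for an IRN during wear.

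SAP 4.7 treats short wear only as a reason why the AF proportion may be underestimated, not as a source of association between a watch result and AF. At stake is the reading of a secondary table: whether a result during wear marks out participants with AF, which bears on the research question in protocol 2.1.

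**Working it through.** **The plan's own figure.** The documents give no alpha, power or sample size for these tests. The nearest stated figure is the confidence interval width in SAP 1.3. Using 2 × 1.96 × √(p(1−p)/n) at p = 0.5, the width is 0.098 at n = 400, 0.113 at n = 300 and 0.139 at n = 200. These match the SAP. I use n = 400 and assume a two-sided 5% level.

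**A case that can be checked by hand.** All rates here are assumptions.
- Wear: 80% wear the patch for 7 days and 20% for 1 day.
- AF: 20% of participants are always detected, 50% are detected with probability 1 − exp(−0.2 × days), and 30% never.
- ECGs: exactly 2 a day, each Inconclusive with probability 0.05 regardless of AF.

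1. AF at 7 days: 0.2 + 0.5 × (1 − e^−1.4) = 0.577. At 1 day: 0.2 + 0.5 × (1 − e^−0.2) = 0.291.
2. At least one Inconclusive at 7 days: 1 − 0.95^14 = 0.512. At 1 day: 1 − 0.95^2 = 0.0975.
3. With an Inconclusive: 0.8 × 0.512 = 0.410 wore 7 days and 0.2 × 0.0975 = 0.0195 wore 1 day. AF = (0.410 × 0.577 + 0.0195 × 0.291) / 0.429 = 0.564.
4. Without one: 0.8 × 0.488 = 0.390 and 0.2 × 0.9025 = 0.1805. AF = (0.390 × 0.577 + 0.1805 × 0.291) / 0.571 = 0.486.

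The difference is about 8 points, although AF and the result are independent at each length of wear. At n = 400 its standard error is √(0.52 × 0.48 × (1/172 + 1/228)) = 0.050. The expected z is about 1.5, and the test rejects in about a third of such studies.

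**Simulation with spread-out wear.** The AF model is the same. A stated share wears 7 days and the rest are uniform from 1 hour to 7 days. ECGs are Poisson with mean 2 a day, each Inconclusive with probability 0.05 or 0.10. For the IRN row, IRNs occur at 0.1 a day, unrelated to AF. There are no prompted ECGs. The table gives rejection under no link at n = 400.

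| Share wearing 7 days | Inconclusive row, chi-squared | IRN row, chi-squared | Stratified by wear |
|---|---|---|---|
| 100% | about 5% | about 5% | about 5% |
| 80% | 9–17% | about 10% | 4–7% |
| 60% | 19–34% | about 20% | 4–7% |

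Other AF patterns widen the range for the Inconclusive row. With 10% on short wear, rejection is 5–8% when part of the AF is persistent and 10–27% when all of it is paroxysmal. With 25% on short wear, the figures are 7–21% and 31–73%.

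**Prompted ECGs (ECG-app rows only).** With everyone at 7 days, one IRN a week in each AF participant gives 7–8%, and 0.5 a day gives 38–43%. At 80% full wear the figures are 20–33% and 59–75%. Across the settings at 80% full wear, the spurious AF difference runs from 3 to 15 points. If prompting occurs only in the 20% with always-detected AF, the 80% figures fall to 13–19% and 22–35%.

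**Minimum wear.** With wear uniform from 1 hour to 7 days and no prompted ECGs, a 2-day minimum gives 6–8% with partly persistent AF and 13–23% with all-paroxysmal AF. A 5-day minimum gives about 5–7% in both. The 5-day cut does not remove the prompted-ECG part: about 7% remains at one IRN a week and 30–38% at 0.5 a day.

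**Stratifying the ECG-app rows.** Stratifying by wear alone leaves up to 39% when prompted ECGs run at 0.5 a day. Stratifying by recording count gives about 5% in the same model. But if every Inconclusive result leads to one repeat ECG, that test rejects 15–23% at 0.5 IRNs a day, or 7–11% if half do. Neither adjustment is clean in all settings.

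**The case against.** A reader might infer that these tests reject because of wear length and prompted ECGs rather than because of any link. The documents do not support that. Protocol 6.0 describes the IRN as flagging rhythms suggestive of AF, so a real link is expected in the IRN row. If an IRN occurs in 20–50% of AF participants and 2–5% of others, the crude test rejects in every simulated study even with identical wear. Independence of an Inconclusive result from AF is also only an assumption, since the category includes heart rates over 120. The point is about attribution, not about the absence of a link.

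The largest figures should not be taken as forecasts. A rate of 0.5 a day means 0.5 × 7 = 3.5 IRNs a week in everyone with AF. Protocol 6.0 says the feature is not meant to notify on every episode, and 1.1 says it checks tachograms over about an hour or more. The ECG-app rows may also have far fewer than 400 participants, because the app is on Series 4 only and Phase 1 collects no watch data. At n = 200 and 80% full wear, rejection is 7–48% across the settings.

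The minimum-wear analyses would deal with most of the wear component if applied to these tests. That stands, but the SAP does not say so.

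Finally, the study has no pre-specified hypotheses, these are example rows within sub-analyses, and chi-squared does answer the marginal question of whether the proportions differ. All true. The SAP nevertheless commits to testing for significant differences, and the marginal difference will be read as information about the watch result.

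**Conclusion.** The point holds as a limited one. For subgroups defined by a result during patch wear, the unadjusted chi-squared test mixes any link between result and AF with unequal wear. In the ECG-app rows it also mixes in IRN-prompted recordings if IRNs are frequent. A rejection, or a difference in the reported proportions, cannot be attributed to the link alone.

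The size is uncertain because the documents give no wear distribution, AF pattern, IRN rate or Inconclusive rate. It is negligible if nearly everyone wears the patch for 7 days and prompting is rare. It is material (9–34% against a nominal 5% in the main scenarios) if 20–40% stop early. Objectives 1a and 1b, their confidence intervals and the sample size are not affected. The change is worth making because it is cheap.

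**What to change.** In SAP 4.3 and protocol 10.3.3, for the during-wear subgroups only:

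- Replace the crude chi-squared test with a Cochran-Mantel-Haenszel test stratified by analysable wear-time band. Use the SAP's own cut-points of 6 hours, 1, 2 and 5 days, plus a band for full wear. Report the AF proportions within those bands.
- Restrict the ECG-app rows to Series 4 users with Phase 2 data. Others have no recordings from which status during wear can be determined.
- For the ECG-app rows, add a sensitivity analysis that also adjusts for the number of recordings during wear. State that this count can itself be raised by AF (through IRNs) or by repeats after an Inconclusive result, so it supplements the wear-stratified test and does not replace it.
- Say whether the minimum-wear analyses also apply to these comparisons.

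Chi-squared tests for baseline subgroups can stay.

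The cost is SAP wording and a few lines of code. Analysable wear time is already needed for the 1-hour rule, and Phase 2 collects ECG app results (protocol 7.9). Stratification loses some power. In the simulations with a true IRN–AF link, the stratified test still rejected in at least 99% of runs.
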